The same provider team caring for the patient in the clinical CINEMA program is the same study team doing the research. Each individual who will be obtaining informed consent is listed on the study team list and several of these same individuals are also clinical staff who will be doing the CGM fitting and defitting. Adjustment of medication and other medical recommendations are based on standard of care clinical judgement and practice and is determined in each specific patient situation based on standard of care clinical practice. Patients are followed up in the CINEMA clinical program by the nurse and diabetes educator usually at 1 month after the first visit and then by the MD at 3 months. However, all CINEMA patients may be in contact with the study team and physician at any time, including to report high or low readings and get advice on medical changes needed. CINEMA is designed to allow real-time patientprovider contact via phone or email with real-time adjustments to medications per standard of care in the clinical program (regardless of research participation). Since the study team physician is identical to the patient's personal physician, and the study nurses and diabetes educator are identical to the patient's clinical team, data are available for medical decision making. The CINEMA team uses cloudbased web apps for the CGM devices in clinical use to view data. Both the nurse navigator and certified diabetes educator (study team/clinical care team) monitor the summary data for each CGM device every 2 weeks on a rotating basis. Actionable values are identified either through routine review of the CGM data or when a participant alerts the study team to a value requiring further attention (see description below). If further discussion/attention is needed by a physician, the CINEMA physician (who is both a study member and the patient's clinician) is contacted by phone, email, or pager to address the issue.

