A high CGM reading is defined as a blood glucose >180 mg/dl and low is defined as blood glucose <70 mg/dl. When high and low levels are reported by the patient and/or identified by the treating providers (identical to the study team), then medical advice is provided to the patient (as per routine standard clinical practice) to address the high and low values. For example, if a participant is alerted to a mildly low glucose value (<70 mg/dl but >30 mg/dl), the participant is instructed to continue to monitor their blood glucose using the CGM. If a participant is alerted to a lower glucose value (<60 mg/dl) or they have symptoms of hypoglycemia (such as dizziness, lightheadedness, severe fatigue, or sweating), they are instructed to eat something with a starch (e.g., a wheat cracker) or drink a few ounces of fruit juice and recheck their blood glucose with the CGM device. If a participant is alerted to a mild to modestly high glucose value (>180 mg/dl but <300 mg/dl), the participant will be instructed to continue to take current medications as prescribed, avoid eating high glycemic foods, and continue to monitor their blood glucose with the CGM device. If a participant is alerted to severely high glucose value (>300 mg/dl but <500 mg/dl), the participant will be instructed to continue to take current medications as prescribed, avoid eating high glycemic foods, drink 1 to 2 L of water over the next 2 to 4 hours, continue to monitor their blood glucose with the CGM device. If the blood sugar does not decrease to <300 mg/dl over the next 2-4 hours, they may require urgent care, so the participant will be referred for immediate medical attention and instructed to go to the nearest emergency room. Should any participant report very severe hyper- (>500mg/dl) or hypoglycemia (<55 mg/dl that does not improve with the aforementioned home actions) that may require urgent care, the participant will be referred for immediate medical attention and instructed to go to the nearest emergency room. In such a situation, or when a participant requires medical advice related to the management of their type 2 diabetes,

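### The lower bound of the mildly-low glucose band (30 mg/dl) conflicts with the treat-and-recheck rule below 60 mg/dl; a minor safety-wording correction

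*Combined protocol and SAP*

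**What the plan says.** The Study Procedures section defines a low reading as under 70 mg/dl and then describes three steps on the low side.

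- **Monitor:** "if a participant is alerted to a mildly low glucose value (<70 mg/dl but >30 mg/dl), the participant is instructed to continue to monitor". No other action is attached to this band.
- **Treat and recheck:** "If a participant is alerted to a lower glucose value (<60 mg/dl) or they have symptoms of hypoglycemia", then "they are instructed to eat something with a starch (e.g., a wheat cracker) or drink a few ounces of fruit juice and recheck".
- **Emergency room:** very severe "hypoglycemia (<55 mg/dl that does not improve with the aforementioned home actions").

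The steps are introduced as examples, after a general statement that "medical advice is provided to the patient (as per routine standard clinical practice) to address the high and low values".

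On the high side, the same paragraph uses separate tiers: "If a participant is alerted to a mild to modestly high glucose value (>180 mg/dl but <300 mg/dl") and then "If a participant is alerted to severely high glucose value (>300 mg/dl but <500 mg/dl"), with emergency referral above 500 mg/dl.

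The same section has the nurse navigator and diabetes educator "monitor the summary data for each CGM device every 2 weeks on a rotating basis". Otherwise a value is acted on when the participant brings it to the team.

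**The concern.** Two consecutive sentences give different instructions for the same readings, and neither says which takes precedence. A participant without symptoms at, say, 45 mg/dl falls in the band whose only advice is to keep watching the CGM. The same participant is also below 60 mg/dl, where the advice is carbohydrate and a recheck.

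The bound also sits badly with the words around it. The second sentence concerns a lower value than the first. A value lower than a band that ends just above 30 would be 30 or less, yet the second rule starts below 60.

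What is at stake is the clarity of a safety instruction during the 90 days of unblinded Phase 2, when participants see their own readings. Staff review is scheduled about six times in that period. Between reviews, the participant's own reaction to a low value matters, and a mild label with advice only to monitor could delay it.

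**Working it through.** The plan gives no figure to reproduce. The check lists whole mg/dl readings under each rule as written in Study Procedures.

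**Inputs**
- Monitor: >30 and <70
- Treat and recheck: <60, or symptoms at any value
- Emergency room: <55 and not improving after home actions
- High-side tiers: >180 to <300, >300 to <500, and >500
- Phase 2 length 90 days; CGM summaries reviewed every 14 days

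**Overlap on the low side**

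| Readings | Range | Count |
|---|---|---|
| Monitor band | 31–69 | 69 − 31 + 1 = 39 |
| Monitor band and also <60 | 31–59 | 59 − 31 + 1 = 29 |
| Monitor band and not <60 | 60–69 | 39 − 29 = 10 |
| Monitor band and also <55 | 31–54 | 54 − 31 + 1 = 24 |

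So 29 of the 39 readings fall under both rules and 10 are monitor-only. The 24 readings from 31 to 54 carry the mild label, but they also lie in the range that leads to emergency referral if home actions fail. Readings of 55 to 59 fall under the treat-and-recheck rule but not the emergency criterion.

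**Which rule is meant to govern**
- The second sentence is worded as a step down from the first.
- The emergency criterion depends on home actions having failed. On the low side, the only corrective home action described is starch or juice. The criterion therefore presupposes that someone below 55 has already been told to treat.

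Both features point to treatment below 60. On that reading, the bound of 30 misstates the range in which monitoring alone is advised.

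**High side for comparison.** The tiers cover 181–299, 301–499 and 501 upward. They share no value; exactly 300 and exactly 500 are left unassigned.

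**Effect of changing the bound**
- With >=60 and <70, the monitor band is 60–69 (10 readings). It shares nothing with <60, and the two rules together cover every value under 70.
- With >60, a reading of exactly 60 would be left out, so >=60 is the better form.

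**Scheduled reviews in Phase 2:** 90 / 14 = 6.4, about 6.

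**The case against.** The strongest defence is that the paragraph has one workable reading. Monitoring and eating are compatible. A participant at 45 mg/dl who follows both sentences watches the CGM, takes juice and rechecks. No value below 60 lacks a treatment instruction. This stands, and it limits the point to an inconsistent bound.

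Other parts of the defence also stand:
- The bands illustrate routine advice from the patient's own clinical team; they are not presented as a fixed algorithm.
- Symptoms prompt treatment at any value. Staff can be contacted at any time, and a 24-hour nurse line and 911 are available.
- The participant instruction sheets named in Study Procedures are not part of the document, so it is unknown whether any participant sees the figure of 30.
- The high-side tiers are loosely drafted too, since they omit 300 and 500. The contrast with the low side is therefore only supporting evidence.
- The very-severe label applies below 55 only when the value fails to improve. Calling such a value mild at first is awkward but not a strict contradiction.

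What the defence does not do is explain the bound. If the rule below 60 governs, a lower limit of 30 on the monitoring band serves no purpose and misdescribes it.

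A reader might go further and make three inferences that the documents do not support:
- **Participants at 31–59 mg/dl are told not to treat.** The next sentence tells them to treat.
- **The 29-of-39 count measures risk.** It counts whole numbers in an interval. The plan gives no hypoglycaemia rate, and entry requires HbA1c of at least 7% with no insulin in the past 3 months.
- **The 30 is a misprint for 60.** That is plausible, but nothing in the document states 60 as the intended lower bound.

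**Conclusion.** The point holds as a minor correction to safety wording. The monitoring band and the treat-and-recheck rule overlap on 31–59 mg/dl, and only 60–69 mg/dl is monitor-only. The stated bound of 30 is inconsistent with the escalation in the same paragraph, and no other part of the document corrects it.

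The overlap is certain if the digit is correct as printed; because the point rests on one number, it should be checked against the source PDF. That the rule below 60 should govern is an inference from the wording, though a strong one. The number of participants affected cannot be estimated, and the safeguards keep the practical risk small. There is no effect on the endpoints, sample size or analysis.

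**What to change.** In the sentence on mildly low values, replace the lower bound of >30 mg/dl with >=60 mg/dl. The low side would then read:

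- at least 60 and under 70 mg/dl, without symptoms: continue to monitor;
- under 60 mg/dl, or symptoms at any value: take starch or juice and recheck;
- emergency criterion (under 55 mg/dl and not improving after home actions): unchanged.

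The clinical investigators should confirm the bound, with a check against the source PDF. The participant instruction sheets and training documents should be compared with the corrected text. The cost is a one-line protocol correction and a document check, with no change to visits, sample size or analysis.

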This investigation is a 2-phase cross-over study with patients serving as their own controls. The demographics, medical history, anthropometric and laboratory data are collected from the electronic medical record at baseline for each patient. During Phase 1 (10 days), the patient wears the Dexcom G6 Pro CGM in blinded mode and is unaware and unable to access the CGM data. The patient performs standard care, self-monitoring with twice daily glucose checks using standard finger-sticks and a glucometer device. During this phase, the medical providers are also blinded to the CGM data and continue standard care without any specific intervention. This 10 day phase is meant to establish a

baseline of CGM data including average glucose, time in range, and glucose variability; and is designed to represent the participant's baseline glucose control. As the CGM measures glucose almost continuously, there are thousands of data points during the 10 days to establish a baseline. During Phase 2 (3 months), the patient wears the Dexcom G6 Personal CGM in un-blinded mode and the medical providers have access to the data via Clarity and/or direct download via the transmitter. CGM data are collected continuously in this phase and at the end of the phase. Anthropometric and laboratory data (including Hb A1c) measured as part of routine clinical care (not directly as part of the research) are collected from the electronic medical record at the end of Phase 2. Medical providers are also un-blinded and counsel the patient, in part based on CGM data, as appropriate.

All patients will receive usual care which will include individual and virtual lifestyle education, virtual support group, M.D. visits, medication interventions, referrals to support programs outside the scope of CINEMA program and nursing support.

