The primary outcome is change in average glucose (mg/dl) measured by the CGM between Phase 1 and Phase 2. Secondary outcomes include change in time in range (TIR), glucose variability (GV), and glucose management indicator (GMI), measured by CGM, as well as changes in anthropometric, laboratory, medication, and survey data, between Phase 1 and Phase 2, as detailed below in "Data to be collected." As this is a pilot/feasibility study, a formal sample size analysis is not applicable. Nonetheless, we expected 60 participants to be sufficient to observe differences in average glucose between baseline and follow-up given that the baseline data contains ~2500 data points for average glucose during the 10 day phase 1 and the 3 month follow up contains several times that number of data points.

Study Procedures

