The total duration of the study will involve 100 days of collected data for each participant. This includes the Phase 1 (10 days blinded) and Phase 2 (90 days unblinded) portions of the study. A total of three study visits are required for participation. During the patient's clinical visit, a research study member will approach them about study participation. If willing to participate, the patient will spend approximately one hour engaging in research-related activities- including informed consent, DexCom G6 Pro fitting, and completing baseline study questionnaires. The second study visit will occur at the end of Phase 1 and will require approximately 45 minutes for returning the blinded DexCom G6 Pro device, fitting of the unblinded DexCom G6 Pro device, and instructions for using the new CGM device. The final visit will occur at the end of Phase 2 and requires approximately 45 minutes. At this study visit, the participant will return the CGM device and complete the study questionnaires. Usage of the Dexcom G6 CGM will not require additional time beyond normal clinic visitation and fitting. The participant will not be financially responsible for devices that are stolen, broken, or lost. After the study is completed, participants will be eligible for clinical prescription of a CGM.

Data to be Collected

Data collected within this study will include continuous glucose monitoring data, laboratory data, medication data, and survey data, as detailed below.

CGM:

- a. Average glucose (mg/dl) primary outcome
- b. Time in range (%)
- c. Glucose variability (standard deviation, mg/dl)
- d. Glucose management indicator (%)

Laboratory:

- a. Hb A1c
- b. Total cholesterol
- c. LDL-cholesterol
- d. HDL-cholesterol
- e. Triglycerides
- f. Systolic and diastolic blood pressure
- g. Body mass index

Medication data:

a. Number of medication changes (add, subtract, dose change)

Survey data:

A total of four surveys will be provided to research participants:

- a. The International Physical Activity Questionnaire
- b. Glucose Monitoring Satisfaction Survey
- c. Picture Your Plate Survey
- d. Diabetes Distress Screening Scale

Data Analysis Plan

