Baseline characteristics of the study cohort will be reported. Each participant will have one data point with their total average (reported by the CGM device) at baseline, 30 days, 60 days, and 90 days. The primary and secondary outcomes will be analyzed using paired sample t-tests since participants will serve as their own controls. As this is a pilot/feasibility study, a formal sample size analysis is not applicable. Nonetheless, we expected 60 participants to be sufficient to observe differences in average glucose between baseline and follow-up given that the baseline data contains ~2500 data points for average glucose during the 10 day phase 1 and the 3 month follow up contains several times that number of data points.

Risks to Research Participants

Insertion of the sensor wire: Participants in the study will be using the Dexcom G6 continuous glucose monitoring device, which has known risks. There is a chance that a sensor wire could break or detach during insertion, remaining under the skin. While uncommon, insertion of the sensor can cause infection, bleeding, or pain. Previous clinical studies have also shown slight redness and swelling following insertion of the sensor wire.

Adhesive patch: Participants using the Dexcom G6 may experience local skin irritation caused by the device's adhesive patch.

Risks of CGM malfunction/inaccuracy: There may be a risk of relying on the CGM for medical management, as there is a possibility that an incorrect reading or incorrect use of the device could lead to a medical problem. In the event that the CGM device is registering possibly inaccurate readings, we will ask the participant to confirm blood glucose using a fingerstick test (as per current standard of care). If the device is judged to be defective, it will be removed by the participant and a new device will be reinserted (as per current standard of care).

Study Questionnaires: Research participants may experience discomfort while completing questionnaires throughout the study. Participants may skip any questions that they are uncomfortable answering.

Confidentiality: Any time information is collected about you there is a potential risk for breached confidentiality. While this risk is small, it is possible that others improperly access your information. For more information on how the study team will ensure this is a minimal risk please see the data management and confidentiality section.

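### Glucose variability is tested only as a raw SD over an unstated Phase 2 window, so a fall in SD alone cannot show improvement beyond the fall in mean glucose

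*Combined protocol and SAP*

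**What the plan says.** - **Primary outcome (Study Design).** "The primary outcome is change in average glucose (mg/dl) measured by the CGM between Phase 1 and Phase 2".
- **Place of variability (Study Design).** "Secondary outcomes include change in time in range (TIR), glucose variability (GV), and glucose management indicator (GMI), measured by CGM". It is thus a named secondary outcome, assessed as a change between the phases.
- **Definition (Data to be Collected, CGM list).** "Glucose variability (standard deviation, mg/dl" is the whole definition. No CV or other mean-adjusted measure is listed. Average glucose is in the same list.
- **Test (Data Analysis Plan).** "The primary and secondary outcomes will be analyzed using paired sample t-tests since participants will serve as their own controls". No adjustment for mean glucose is described.
- **Length of the phases (Study Timeline).** "This includes the Phase 1 (10 days blinded) and Phase 2 (90 days unblinded) portions of the study". Study Design says that Phase 1 is there to establish a "baseline of CGM data including average glucose, time in range, and glucose variability".
- **Time points (Data Analysis Plan).** Each participant has "one data point with their total average (reported by the CGM device) at baseline, 30 days, 60 days, and 90 days". This sentence is written for the average only. It does not say whether the later values are 30-day blocks or cumulative, and nothing states which stretch of Phase 2 supplies the SD.

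**The concern.** The trial hopes to see mean glucose change. If it falls, and high and low readings come down roughly in proportion, the SD in mg/dl falls with it. A significant SD result would then mostly restate the primary result, yet it could be reported as a second finding that glucose became steadier. The plan names no analysis that would separate the two.

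The window is a different issue and acts in the opposite direction. An SD taken over a longer period includes slow movement of glucose between days and weeks that a 10-day record shows less of. If the Phase 2 SD covers 30 or 90 days, it tends to be somewhat higher than a 10-day SD from the same patient under the same control, and a real fall would be understated.

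At stake is what the trial can conclude about variability, not its primary analysis.

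**Working it through.** **Inputs from the documents.** Up to 60 participants; Phase 1 of 10 days; Phase 2 of 90 days; SD in mg/dl; paired t-test. The plan gives no expected SD, CV, size of change or SD of change for variability, so it has no figure of its own to reproduce. Every glucose value below is an assumption, shown as a range.

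**1. Proportional scaling.** If the CV (SD / mean) is constant, change in SD = CV × change in mean.
- CV 25%, mean falls 10 mg/dl: 0.25 × 10 = 2.5 mg/dl.
- CV 33%, mean falls 30 mg/dl: 0.33 × 30 = 9.9 mg/dl.

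The SD falls by 2.5 to 9.9 mg/dl, and the CV does not change.

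**2. How often the planned test would be significant under step 1.** Two-sided 5% paired t-test (level assumed), n = 60, noncentrality = change × √60 / (SD of paired change), CV 25%, SD of paired change assumed at 8 to 12 mg/dl.
- Mean falls 10 mg/dl (SD falls 2.5): noncentrality 2.42 to 1.61, probability 0.66 to 0.36.
- Mean falls 20 mg/dl (SD falls 5.0): noncentrality 4.84 to 3.23, probability 1.00 to 0.89.

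In each case absolute spread has really fallen and relative spread has not changed.

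**3. Pure downward shift.** Assume an SD of 45 and a mean that falls from 180 to 160 mg/dl, with every reading moving by the same amount. The SD stays at 45. The CV goes from 45 / 180 = 25% to 45 / 160 = 28.1%. Here the SD shows no change and the CV shows a worsening.

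**4. Window length alone, no true change.** Two models were used.

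*Independent 10-day windows.* Let s be the within-window SD (45 to 55), b the SD of the window means (8 to 20) and k the number of 10-day windows. Rise in SD = √(s² + b²(1 − 1/k)) − s.

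| Period | Smallest (s = 55, b = 8) | Largest (s = 45, b = 20) |
|---|---|---|
| 30 days, k = 3 | √(3025 + 42.7) − 55 = 0.4 | √(2025 + 266.7) − 45 = 2.9 |
| 90 days, k = 9 | √(3025 + 56.9) − 55 = 0.5 | √(2025 + 355.6) − 45 = 3.8 |

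*Day-level model.* Within-day SD 45, SD of day means 10 to 20, correlation between successive days 0 to 0.9. Expected SD = √(within-day SD² + day-mean SD² × (1 − average correlation between days in the window)). The rise is 0.1 to 1.2 mg/dl from 10 to 30 days, and 0.1 to 2.3 mg/dl from 10 to 90 days.

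**5. Both effects together.** Day-level model with day-mean SD 15, correlation 0.8, and the mean falling from 180 to 160 mg/dl with proportional scaling. The 10-day baseline SD is 46.1. In Phase 2 a matched 10-day SD is 41.0, a 30-day SD is 41.6 and a 90-day SD is 42.0. The matched comparison shows a fall of 46.1 − 41.0 = 5.1 mg/dl; the 90-day comparison shows 46.1 − 42.0 = 4.1. The longer window hides about 1 mg/dl of the fall, which itself is wholly proportional to the mean.

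**The case against.** The strongest reply is that the SD is a legitimate measure of absolute spread. If it falls by 4 or 5 mg/dl, absolute variability did fall and the test is right to detect it. **This stands.** The probabilities in step 2 are not false-positive rates. They show how often the SD test would be significant when relative spread has not changed. For the same reason the SD should not be demoted to a descriptive measure: the CV has the mirror weakness, as step 3 shows.

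A reader might infer that the SD falls automatically whenever the mean falls. The documents do not support that. It holds under proportional scaling and fails under a pure shift, and they contain no data on which pattern these patients follow.

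A reader might also infer that variability cannot be told apart from the primary result at all. That is too strong. Mean and SD are both collected for each participant, so the CV can be derived. What is missing is a plan to do so. Nor can the unequal windows be a reason why the SD follows the mean, since they push it upward.

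It can fairly be said that the plan never states that a 10-day SD will be compared with a longer one. The time points "total average (reported by the CGM device) at baseline, 30 days, 60 days, and 90 days" concern the average. The unequal comparison is the natural reading, and the defect that can be stated firmly is that the window is not given.

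Finally, this is one of many secondary outcomes in a self-described pilot, and no passage says that a fall in SD will be presented as independent of the mean. That limits the weight of the point. It does not remove it, because the plan offers no other means of interpreting the SD result.

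**Conclusion.** The point holds in a limited form. With the raw SD as the only variability measure and no reference to the mean, a significant fall in SD would not show that variability improved beyond the fall in mean glucose. The size depends on proportional scaling and on an assumed CV of 25% to 33%: 2.5 to 9.9 mg/dl for a fall of 10 to 30 mg/dl in the mean. Under a pure shift this component is zero and the CV rises instead, so the two measures need to be read together.

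The unstated window is a separate and usually smaller matter in the opposite direction. It is worth about 0.4 to 2.9 mg/dl for 30 days and 0.5 to 3.8 for 90 days under independent 10-day windows, or 0.1 to 1.2 and 0.1 to 2.3 under the day-level model. It can partly mask a true fall.

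The primary outcome is not affected, and nothing is lost irretrievably. This is an inexpensive improvement to a named secondary outcome.

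**What to change.** In Data to be Collected, keep the SD and add the CV (100 × SD / mean) as a co-reported variability measure.

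In the Data Analysis Plan, state three things before analysis begins:
1. Change in mean, SD and CV will be reported together.
2. Reduced variability independent of mean glucose will be claimed only if the CV also falls.
3. SD and CV will be computed over 10-day windows in both phases, for example as the average of the 10-day values within each Phase 2 period.

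**Cost.** A few sentences in the plan, with no new visits, participants or measurements. The CV follows directly from values already listed. The 10-day Phase 2 summaries do need work: they must be exported for each window or computed from the CGM readings, and the documents do not say that reading-level data are already held. The variability result may also look less favourable, and a fall in SD that is less than proportional to the fall in the mean would not support the independent claim.

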during office hours (8 am – 5 pm weekdays), the participant may contact the CINEMA office by [contact]) or email ([contact]). For questions about their CGM device they will be instructed to call the Dexcom Care program for technical support ([name]). Outside of office hours, the participant will be instructed to call the on-call 24/7 nurse help line [contact]) or 911 if there is a serious emergency. It is not expected that insulin would be needed for a participant during the study since all participants by design are not using insulin at study start.

The Dexcom G6 Pro continuous glucose monitoring device is a device approved by the U.S. Food and Drug Administration (FDA) and will be implemented in the study. It is approved for the management of diabetes in persons age 2 and older regardless of background diabetes therapy (including insulin). In addition to glucose monitoring data collected by the Dexcom G6 Pro CGM, the study personnel will also collect laboratory data, survey data, and medication data. Four types of surveys will be administered throughout the research study: The Picture Your Plate Survey (PYP), Diabetes Distress Scale (DDS), International Physical Activity Questionnaire (IPAQ), and Glucose Monitoring Satisfaction Survey (GMSS). At study Visit 1, the research team will administer the Picture Your Plate Survey, Diabetes Distress Scale, and International Physical Activity Questionnaire. At study Visit 3, the research team will re-administer these surveys in addition to the Glucose Monitoring Satisfaction Survey swill be completed via pen and paper or iPad. Participants will also be offered the option to take home paper copies of each survey and return them completed at the following study visit. Throughout the research study, medical and laboratory information will also be collected from the patient's electronic medical record.

Study Timeline

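### The number of medication changes is assigned a paired t-test between a 10-day and a 90-day phase, so the test compares unequal exposure or, for a single total, has no Phase 1 value to pair

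*Combined protocol and SAP*

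**What the plan says.** Under Study Design, the secondary outcomes include "changes in anthropometric, laboratory, medication, and survey data, between Phase 1 and Phase 2". Data to be Collected gives one medication item: "Number of medication changes (add, subtract, dose change"). The Data Analysis Plan then applies one method to everything, without exceptions: "The primary and secondary outcomes will be analyzed using paired sample t-tests since participants will serve as their own controls".

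The phase lengths are in Study Timeline: "This includes the Phase 1 (10 days blinded) and Phase 2 (90 days unblinded) portions of the study". Enrolment takes place at an ordinary appointment, since it is during the patient's "clinical visit, a research study member will approach them about study participation". In Phase 1 the providers "continue standard care without any specific intervention"; in Phase 2 they may use the CGM results when adjusting treatment (Study Procedures).

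On timing, Study Design says that anthropometric and laboratory data "are collected from the electronic medical record at the end of Phase 2"; neither that list nor the baseline list names medication changes. Study Procedures says that study personnel will collect medication data, but not over what period, and adds: "Throughout the research study, medical and laboratory information will also be collected from" the patient's record. The baseline, 30, 60 and 90 day values in the Data Analysis Plan are for the CGM average.

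Study Procedures gives the Glucose Monitoring Satisfaction Survey at Visit 3 and not at Visit 1.

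**The concern.** A paired t-test on raw values asks whether the mean difference is zero. For average glucose, time in range, a laboratory value or a repeated survey score, zero difference is a sensible null, because the quantity does not grow with the length of observation. A count of events does grow. With 10 days against 90, equal raw counts would mean a ninefold fall in the daily rate, so the null tested is not the null of unchanged prescribing.

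Two readings of the plan are open: a count in each phase, or one count over the study. The stated test is unsuitable on both. At stake is a statement in the report that medication changes rose (or fell) between phases when the daily rate did not move. That would matter to a reader, because treatment adjustment in Phase 2 is one of the explanations for any change in glucose.

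**Working it through.** The plan states no rate of medication changes and no significance level, so there is no figure of its own to reproduce.

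**Inputs from the documents.** Phase 1 is 10 days and Phase 2 is 90 days (Study Timeline); enrolment is up to 60 (Number of Research Participants).

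**Assumptions.** L = 0.05, 0.1, 0.25 or 0.5 changes per participant per 90 days; the same daily rate in both phases; independent Poisson counts; two-sided 5% level. Simulations used 40,000 trials per setting unless noted.

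**1. Count per phase, Visit 1 changes left out.** The Phase 1 mean is 10 × L/90 = L/9 and the Phase 2 mean is L. The ratio is 9 and the expected difference is L − L/9 = 8L/9. The standard error with n participants is √((L + L/9)/n), and the chance of a significant increase is roughly Φ(difference/SE − 1.96). For L = 0.1 and n = 60: difference 0.0889, SE = √(0.1111/60) = 0.0430, ratio 2.07, Φ(0.11) ≈ 0.54. Simulation of the t-test itself gives:

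| L per 90 days | 0.05 | 0.1 | 0.25 | 0.5 |
|---|---|---|---|---|
| Phase 1 mean (L/9) | 0.006 | 0.011 | 0.028 | 0.056 |
| Normal approximation, n = 60 | 31% | 54% | 90% | 99.6% |
| Simulated false increase, n = 60 | 24% | 56% | 94% | 99.9% |
| Simulated false increase, n = 40 | 10% | 35% | 79% | 98% |
| Clustered changes, n = 60 | 5% | 27% | 78% | 97% |
| Clustered changes, n = 40 | 1% | 10% | 55% | 88% |

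The nominal figure in that direction is 2.5%. In the clustered rows, half of the contacts produce two changes at once, with the same mean. The n = 40 rows illustrate a smaller analysed sample.

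**2. Count per phase, Visit 1 changes placed in Phase 1.** The difference changes sign when Visit 1 changes average more than 8L/9 per participant: 0.04, 0.09, 0.22 and 0.44 for the four rates. Simulated at n = 60:

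| L per 90 days | 0.05 | 0.1 | 0.25 | 0.5 |
|---|---|---|---|---|
| 5% of participants have one Visit 1 change: increase | 2% | 9% | 66% | 98% |
| 5%: decrease | 3% | 0.3% | 0% | 0% |
| 20% of participants have one Visit 1 change: increase | 0% | 0% | 4% | 60% |
| 20%: decrease | 73% | 38% | 2% | 0% |

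So the placement of changes made on one day can move the result from a significant increase to a significant decrease.

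**3. One total over the study.** Each participant has one number and no Phase 1 partner. A one-sample test against zero can be computed. With 60 participants it is significant in 81% of trials at a mean of 0.1 changes per 100 days and 99.9% at 0.25 (20,000 trials), but this says only that some changes occurred.

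**4. Does dividing by days repair the t-test?** It removes the bias in the mean, but a 10-day phase with few events gives very skewed per-day values. At n = 60 and equal true rates, the test still rejects in 23%, 42%, 19% and 10% of trials, against 5%.

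**5. The satisfaction survey.** With one administration, at Visit 3, there is no baseline score to subtract. The sentence in the Data Analysis Plan therefore needs a stated exception regardless of the medication count.

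**The case against.** The strongest reply is that equal daily rates are not what this design leads one to expect. Phase 1 is ordinary care with no specific intervention, usual clinic follow-up is at about 1 and 3 months, and Phase 2 allows CGM-based adjustment. On that view a higher count in Phase 2 is by design, and calling it false is artificial. This stands as far as the percentages go: they describe the test under an assumed null and do not predict this clinic. It does not rescue the test, because a difference expected for reasons of duration and scheduling is no evidence about prescribing behaviour.

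Second, every rate is assumed, and the results run from little or no inflation to near certainty, with either sign. That also stands. What comes from the documents is the 10 to 90 day ratio and the missing rule for visit-day changes.

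Third, the counting window is not wholly absent. Visits 1, 2 and 3 bound the phases, and the outcome is tied to those phases. What is unstated is whether a per-phase count is meant and where changes made on a visit day belong.

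Fourth, a sensible analyst would simply report the count. Perhaps so, but the plan as written says to test it.

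A reader might infer that the trial will report a spurious increase. The documents do not support that: they give no rate, and Visit 1 placement can reverse the sign. A reader might also infer that the secondary analyses are unsound as a group. They are not on this ground: the CGM, laboratory, anthropometric and repeated survey measures do not accumulate with phase length.

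**Conclusion.** The point holds for the number of medication changes and, for a simpler reason, for the Glucose Monitoring Satisfaction Survey. Read together, Study Design, Data to be Collected and the Data Analysis Plan prescribe a test that does not fit either reading of the medication count. On a per-phase count the ninefold difference in exposure follows from the documents alone. The false-increase figures at 60 participants (about 24% to 99.9%, or 5% to 97% with clustering) depend on the assumed rates, equal daily rates and the 5% level. On a single total there is no pair.

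The effect is confined to secondary items of a pilot study. The primary outcome, average glucose by CGM, is not affected. It is worth correcting before analysis because the rule is stated, gives a misleading result if followed, and is cheap to change.

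**What to change.** 1. In the Data Analysis Plan, limit paired t-tests to outcomes measured at both baseline (Phase 1 or Visit 1) and follow-up (Phase 2 or Visit 3). This wording keeps the laboratory, anthropometric and repeated survey measures in. Name the number of medication changes and the Glucose Monitoring Satisfaction Survey as exceptions, reported descriptively.
2. Amend the outcome paragraph in Study Design to match, so that medication changes are a descriptive Phase 2 outcome and not a between-phase change, and the satisfaction survey is a Visit 3 measure. Otherwise the two sections would contradict each other.
3. State the counting window and the treatment of visit-day changes. For example: count changes dated from Visit 2 to Visit 3, saying whether both visit days are included; treat changes made at Visit 1 as baseline; only list changes between Visits 1 and 2.
4. Report the number and proportion of participants with at least one Phase 2 change, with an exact binomial 95% confidence interval, and the total count by type (add, subtract, dose change) with the days observed. Make no between-phase test, since the per-day t-test also over-rejects.

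The cost is a few sentences in two sections and the date of each change from the medical record. Visits, sample size and the primary outcome stay as they are. The downside is one fewer significance test: the report will describe medication changes in Phase 2 without claiming a change from Phase 1.
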